	This phase 1b study will investigate the dosing of Betalutin in combination with RTX, whereby RTX is given shortly following Betalutin to capitalise on potential enhanced CD20 expression after Betalutin administration. One phase 2 study evaluating short course cyclophosphamide, hydroxydaunorubicin, oncovin and prednisone (CHOP)-RTX chemotherapy followed by 90Y-ibritumomab tiuxetan (Zevalin®) in treatment-naïve

follicular lymphoma (FL) patients has been reported [Jacobs, 2008]. Fifty-five patients received 3 courses of CHOP-RTX followed by Zevalin® once haematologic recovery was attained. One week following Zevalin administration, four additional weekly doses of RTX were given. The incidences of grade 3/4 neutropenia and thrombocytopenia were 51% and 44% respectively, consistent with previously reported data (prescribing information for RTX), and all patients had full haematologic count recovery by 12 weeks post-Zevalin. The use of RTX six months following Zevalin® administration in previously untreated high tumour burden FL patients was reported to convert all partial responses (PRs) to complete responses (CRs) in one study [Rajguru, 2014], but the optimal duration of rituximab therapy is unknown. Combining Betalutin with RTX may be attractive to patients due to a favourable dosing schedule, and potential for maintaining a good quality of life. We hypothesise that combining Betalutin with RTX could enhance both the response rates and the durability of responses in patients with recurrent FL.

This protocol describes a Phase 1b, open-label, single-arm, dose escalation study of Betalutin followed by RTX in patients with previously treated FL. The purpose of this study is to characterise the safety, tolerability, pharmacokinetics, pharmacodynamics and antitumour activity of Betalutin in combination with RTX.

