#### **Secondary**

- Responses (overall response rate [ORR], CR, PR, stable disease [SD], progressive disease [PD]) as per Cheson 2014
- Duration of response (DoR)
- Progression free survival (PFS)
- Time to progression (TTP)
- Overall survival (OS)
- Monitoring of the anti-drug antibody (ADA) response towards lilotomab, Betalutin and/or RTX

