	The intent-to-treat (ITT) population will consist of all patients who were enrolled and treated with lilotomab/Betalutin, regardless if RTX therapy was initiated. The number and percentage of patients with each response and overall (complete + partial responders) will be presented for each time point for the ITT population.
	Pharmacokinetic, biodistribution and biomarker exploratory analyses will be described in the statistical analysis plan finalised before database lock.
Key dates	The start date of the study (first patient included) was in October 2018.
	The expected accrual time is 18 months.
	Patients will be followed up for up to 25 months (End of study visit) after Betalutin administration.
	Patients in survival follow at time of Protocol version 4.0 approval can have the EOS visit at their next scheduled visit or an earlier convenient time point

CONFIDENTIAL

Protocol Study Number: LYMRIT-37-07

Version 4.0\_04 Oct 2021

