With a lilotomab pre-dose of 40 mg (Arm 1), the recommended dose of Betalutin for phase 2 expansion was 15 MBq/kg. In total, 36 patients have received this regimen (25 with FL); the overall response rate (ORR) is 64% (CR 25%), and 72% (CR 24%) for the FL subset, and the toxicity profile is favourable. The incidence of grade 3/4 neutropenia and thrombocytopenia was 20/36 (56%) for both. Grade 4 neutropenia and thrombocytopenia were reported in 7 patients (19%) and 6 patients (17%) respectively. Of these, there were 2 patients with grade 4 neutropenia lasting >7 days, and 2 with grade 4 thrombocytopenia >7 days.

In Arm 4 (lilotomab pre-dose of 100 mg/m²), the recommended Betalutin dose for phase 2 expansion was 20 MBq/kg. Eight patients have been enrolled; the ORR is 50%. Two FL patients have had a CR. The incidences of grade 3/4 neutropenia and thrombocytopenia were 3/8 (38%) and 4/8 (50%) respectively (there was one grade 4 thrombocytopenia reported). One patient had a DLT of haematuria with thrombocytopenia (platelet count of 40 x 10^9/L) and received a platelet transfusion. A phase 2 expansion cohort is currently enrolling up to 15 patients.

Overall, Betalutin treatment was well-tolerated, with the most common adverse events (AEs) reported being neutropenia and thrombocytopenia which were transient and generally required no intervention. Bruising/bleeding episodes were reported in 3 and 4 patients respectively; only 2 patients required platelet transfusions for bleeding events in association with thrombocytopenia (one with epistaxis and one with haematuria). Overall, 23 patients (39%) developed infections, with urinary and respiratory tract infections (including nasopharyngitis) being most commonly reported (19 patients [32%]). The majority of infections were low grade in nature. The dosing regimen was generally well tolerated, with only 2 infusion reactions reported; both were related to RTX.

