# 3. Objectives and Endpoints

Objectives and related endpoints are described in Table 3-1 below.

Table 3-1 Study objectives and endpoints

Objectives	Endpoints				
Primary					
To evaluate the safety and tolerability of Betalutin in combination with RTX	• Frequency and severity of adverse events (AEs), serious adverse events (SAEs) and changes in laboratory values graded according to CTCAE version 4.03				
Secondary					
To establish a recommended dose of Betalutin in combination with RTX for phase 2 studies in NHL patients	Frequency and severity of AEs, SAEs and changes in laboratory values graded according to CTCAE version 4.03				
To evaluate the preliminary anti-tumour activity of combination treatment based on Investigator assessment of tumour response rates	• Responses (overall response rate [ORR], complete response [CR], partial response [PR], stable disease [SD], progressive disease [PD]) per Cheson 2014 [30]				
To evaluate the duration of tumour control in	Duration of response (DoR)				
patients receiving Betalutin in combination	Progression free survival (PFS)				
with RTX	• Time to progression (TTP)				
	Overall survival (OS)				
To investigate the immunogenicity of Betalutin in combination with RTX	Monitoring of the anti-drug antibodies (ADA) response towards lilotomab, Betalutin and/or RTX				
Exploratory					
To characterise the pharmacokinetics (PK) of Betalutin in combination with RTX	Estimation of the levels of remnant administered radioactivity in blood over time (Betalutin PK)				
To assess the pharmacodynamic effects of Betalutin in combination with RTX	
 
Change from baseline in peripheral blood B-cell, T-cell and NK cell counts, tumour CD20 and CD37 expression
 
Biomarker assessments
 
				
To investigate the biodistribution of Betalutin in combination with RTX	• Estimation of whole-body retention of radioactivity at each imaging time post-injection.				
	• Estimation of the individual organ uptake/retention of radioactivity at each imaging time-point after injection.				
	Calculation of estimated absorbed radiation dose to target organ.				
To evaluate minimal residual disease in patients with a CR	Monitoring of detectable disease to assess early treatment response and detect relapse using next generation sequencing (NGS) (molecular Minimal Residual Disease (MRD))				

CONFIDENTIAL

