#### 10. Statistical Considerations

## **10.1.** Statistical Analyses

The study is a single-arm, open-label study to further assess the risk/benefit of a pre-dose of lilotomab and Betalutin to enhance tumour response to RTX therapy. Six to 12 patients is a reasonable sample size to evaluate any potential safety/tolerability signals and for obtaining preliminary estimates of the response rates and variability of the response rates.

The primary endpoint is the frequency and type of AEs. Study data will be summarised with respect to demographic and baseline characteristics, safety observations and measurements, efficacy observations and measurements (response rates, duration of response, PFS, TTP, OS), and PK measurements. Categorical data will be presented in tables; descriptive statistics will be used to summarise response rates, etc. Patients who have withdrawn from the study, including those who have died, will be counted as having PD for all visits after the time of withdrawal.

The number and percentage of patients with each response, and overall (CR + PR) will be presented for each time point for the ITT population. All data obtained after treatment with lilotomab/Betalutin will be summarized by the dose of Betalutin received and overall doses.

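### ORR is specified only as CR+PR at each of five imaging visits; the plan sets no summary response rate and no confidence interval

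*Combined protocol and SAP*

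**What the plan says.** The synopsis lists among the secondary endpoints: "Responses (overall response rate [ORR], CR, PR, stable disease [SD], progressive disease [PD]) as per Cheson 2014". Table 3-1 in Section 3 lists the same endpoint. Neither place says whether ORR means best response over follow-up or response at a named visit.

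The analysis is in Section 10.1, for the ITT population: "The number and percentage of patients with each response, and overall (CR + PR) will be presented for each time point". The statistical methods entry of the synopsis matches it: "The number and percentage of patients with each response and overall (complete + partial responders) will be presented for each time point for the ITT population". Section 10.1 adds that patients who leave the study, including those who die, "will be counted as having PD for all visits after the time of withdrawal". Results are split by Betalutin dose and also shown for all doses together.

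Other parts of the plan bear on how these rates read:

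- Section 4.1 sets PET/CT plus CT or MRI at Months 3 and 6, and contrast CT or MRI alone at Months 12, 18 and 24.
- Section 7.2 makes disease progression a reason for leaving the study.
- Sections 4.2 and 6.1 start maintenance rituximab at Week 14, after the Week 12 (Month 3) scan.
- Section 10.1 defends the sample size partly as enough for preliminary estimates of response rates and of their variability.
- Section 10.1.2 leaves PK and biomarker analyses to a SAP, and the synopsis adds biodistribution. Neither leaves response to it.

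**The concern.** CR+PR at a visit is the proportion in response on that occasion. It falls as responses end, and it misses a patient whose response was seen only at another visit. With progression ending participation and leavers set to PD, this holds at all five visits. No visit is named as the one that gives the ORR.

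The visits also differ in what they measure. Month 3 comes before maintenance rituximab and the later visits come after it has started. This matters most for the CR rate, because the rationale cites rituximab given after another radioimmunoconjugate, which "was reported to convert all partial responses (PRs) to complete responses (CRs) in one study". Months 3 and 6 have PET as well as CT or MRI, and the later visits do not. Table 9-1 gives separate PET-based and CT-based categories. Section 9.1 names CT or MRI as the required method, but the plan does not say which category enters the table when both exist.

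At stake is the activity read-out. Without a named summary, the choice of figure to quote can be made after the data are seen, in an open-label study with investigator-assessed response. Without an interval, the stated aim of describing variability has no planned output. Duration of response also needs a defined set of responders, which by-visit tables do not supply.

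**Working it through.** **What the plan's figures are.** Two cohorts of 3 to 6 patients give 2 × 3 = 6 and 2 × 6 = 12, which matches the stated size. The plan gives no target ORR, power or precision figure, so there is nothing further of its own to reproduce.

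**How many rates result.** Five visits × (10 MBq/kg, 15 MBq/kg, all doses) = 5 × 3 = up to 15 CR+PR rates.

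**One patient, no model needed.** Take SD at Month 3, PR at Month 6 and PD at Month 12. The patient then leaves and counts as PD at Months 18 and 24. The patient is a responder in one table of five, and a responder under best overall response.

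**A group of 12, no model needed.** Suppose 8 respond at Month 3. By Month 6 one of these has progressed and one patient with SD has reached PR. The Month 3 rate is 8/12, the Month 6 rate is 8 − 1 + 1 = 8, so 8/12, and 8 + 1 = 9 of 12 have responded at some time. Neither visit shows 9/12.

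**An illustration of the fall over time.** Two inputs are borrowed from the earlier single-agent study and are not assumptions of this trial:

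- Section 2.2.2.1: "the overall response rate (ORR) is 64% (CR 25%), and 72% (CR 24%) for the FL subset". With 25 FL patients, 72% is 18/25; with 36 patients, 64% is 23/36.
- Section 2.4: median duration of response above 12 months (Arm 1, n = 28). This is a lower limit, so 12 is the least favourable reading and longer medians are shown beside it.

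Assume that all responses start at Month 3, durations are exponential and nobody responds later. Then

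rate(t) = 0.72 × 0.5^((t − 3)/m), with m the median duration in months.

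For m = 12 at Month 24: 0.72 × 0.5^(21/12) = 0.214.

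| Median duration | Month 3 | Month 6 | Month 12 | Month 18 | Month 24 |
|---|---|---|---|---|---|
| 12 months | 72% | 61% | 43% | 30% | 21% |
| 18 months | 72% | 64% | 51% | 40% | 32% |
| 24 months | 72% | 66% | 56% | 47% | 39% |
| 36 months | 72% | 68% | 61% | 54% | 48% |

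The shape matters too. With median 12 and a Weibull shape of 0.7, 1.5 or 2, the Month 24 rate is 26%, 15% or 9%. Best overall response under the same model is 72% in every row.

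**Precision (Clopper-Pearson 95%).** 8/12: 35% to 90%. 9/12: 43% to 95%. 4/6: 22% to 96%. 3/12: 5% to 57%. No such interval is planned for any response rate.

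**The case against.** Several objections have force.

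- **The data for a summary ORR will exist.** ORR is a listed endpoint, Section 10.1 promises summaries of response rates and duration of response, and best response can be derived from the visit records. This stands. A reader might infer that the trial cannot yield a single ORR, and the documents do not support that. What they show is that none is specified.
- **A fall from 72% to 21% is not a property of this trial.** This stands. It joins two single-agent results with different denominators, reads a median of over 12 months as exactly 12, and ignores the rituximab given here after Betalutin and as maintenance.
- **The rates quoted in the rationale may not be best overall responses.** A reader might infer that the by-visit rates cannot be set beside 64%, 72% or the roughly 50% for rituximab alone because those are best responses. Sections 2.2.2.1 and 2.4 do not say how they were defined, so that claim is not made here.
- **Best overall response has its own faults.** It is never lower than any single-visit rate, it includes maintenance rituximab, and it pools visits with and without PET. By-visit tables keep these apart, and Section 10.1 commits to showing every visit. This stands, and is why the Month 3 rate and the imaging criteria must accompany the summary.
- **The consequence is limited.** The primary endpoint is safety, the phase 2 dose recommendation rests on safety data, and there is no efficacy threshold. The intervals are wide at this size. This also stands.

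What remains is that the stated method gives only rates of current response without intervals, while the plan says that it will estimate response rates and their variability.

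**Conclusion.** The point holds as an under-specified secondary analysis that should be corrected. The plan sets five by-visit CR+PR rates, up to 15 with the dose split, and neither a summary ORR nor an interval. That conclusion rests on the text alone and needs no model. It covers the text available here, in which response is not among the analyses left to the SAP.

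The size can only be illustrated. From 72% at Month 3, the Month 24 rate is about 21% to 48% for median durations of 12 to 36 months under exponential decline with every response starting at Month 3, and 9% to 26% at a median of 12 months under the other shapes tried. Neither the safety conclusions nor the dose recommendation depends on it.

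**What to change.** - Define ORR as best overall response of CR or PR, and the CR rate as best overall response of CR, up to Month 24 and before progression or new anticancer therapy. Use the ITT population, by dose and overall, with exact (Clopper-Pearson) 95% confidence intervals.
- State which response criteria, PET/CT or CT/MRI, apply at each visit.
- Report the Month 3 rate with its exact interval beside the summary, labelled as the rate before maintenance rituximab.
- Keep the by-visit tables as supportive.

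The cost is some analysis wording and one extra table from data already collected, with no change to visits or procedures. The drawback is that best overall response is at least as high as any single-visit rate, so it should be read together with the Month 3 rate.

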#### 10.1.1. Populations for analysis

Intent-to-treat (ITT) population: The ITT population will consist of all patients who were enrolled and treated with lilotomab/Betalutin, regardless if RTX therapy was initiated.

Safety Population: The safety analysis population will include all patients who received at least one dose of any study drug.

PK population: The PK population consists of all patients who have a PK assessment with a sufficient number of evaluable blood samples.

#### 10.1.2. Other Analyses

PK, and biomarker exploratory analyses will be described in the statistical analysis plan (SAP), which will be finalised before database lock. Analyses will be presented separately from the main clinical study report (CSR).

# 12. Appendices

## **Appendix 1: Abbreviations**

AE Adverse events

AESI Adverse events of Special Interest

ADA Anti-drug antibody
ADL Activities of daily living
ADR Adverse drug reaction
ALP Alkaline phosphatase
ALAT Alanine transaminase
AML Acute myeloid leukaemia
ANC Absolute neutrophil count

ARC Antibody-radionuclide-conjugate

ASAT Aspartate transaminase

AUC Area under plasma drug concentration-time curve

β-HCG beta human-chorionic gonadotropinCCLS Covance Central Laboratories

CHOP Cyclophosphamide, hydroxydaunorubicin, oncovin and prednisone

Cmax Maximum plasma drug concentration;

CNS Central nervous system
CR Complete response
CSR Clinical study report
CT Computed tomography

CTCAE Common Terminology Criteria for Adverse Events CVP Cyclophosphamide, vincristine and prednisolone

DC Decay correction factor

DLBCL Diffuse Large B-Cell Lymphoma

DLT Dose limiting toxicity
DoR Duration of response

DOTA Abbreviation/company code for the chelator p-SCN-benzyl-DOTA

IUPAC name: 1,4,7,10-Tetraazacyclododecane-1,4,7,10-tetraacetic

acid, 2-[(4-isothiocyanatophenyl)methyl]

DTPA Diethylenetriaminepentaacetic acid

ECG Electrocardiogram

ECOG Eastern Cooperative Oncology Group

eCRF Electronic Case Report Form EDTA Ethylenediaminetetraacetic acid

Emax Maximum energy

FACT-Lym Functional Assessment of Cancer Therapy–Lymphoma

FDA Food and Drug Administration
FFPE Formalin fixed paraffin embedded

FDG (18F) Fluor deoxy glucose FL Follicular lymphoma

FSH Follicle stimulating hormone

GCP Good clinical Practice

G-CSF Granulocyte colony-stimulating factor

GGT Gamma-glutamyl transferase

GM-CSF Granulocyte-macrophage colony-stimulating factor

HAMA Human anti-murine antibody

#### **CONFIDENTIAL**

HBsAg Hepatitis B surface antigen
HRT Hormonal replacement therapy
Anti-HBc Antibody to hepatitis B core antigen
HIV Human immunodeficiency virus

HLA Human leucocyte antigen

I Iodine

ICF Informed consent form

ICH International Council for Harmonisation

IEC Independent Ethics Committee

IgG Immunoglobulin G

In Indium

INR International Normalized Ratio

iNHL Indolent non-Hodgkin B-cell lymphoma

IRB Institutional Review Board

ITT Intent to Treat IUD Intrauterine device

IUS Intrauterine hormone-releasing system

i.v. IntravenousLDi Longest diameter

Lu Lutetium

Max Maximum

MBq Mega becquerel

MedDRA Medical Dictionary for Regulatory Activities

MHC Major Histocompatibility Complex

MAB Monoclonal antibody
MRD Minimal residual disease
MRI Magnetic resonance imaging

MS Mass spectrometry
MTD Maximum tolerated dose
MDS Myelodysplastic syndrome
NCI National Cancer Institute
NHL Non-Hodgkin Lymphomas
NYHA New York Heart Association

ORR Overall response rate
OS Overall survival
PD Progressive disease

PET Positron-emission tomography PFS Progression-free survival

PK Pharmacokinetic

PPD Individual product of the perpendicular diameters

PR Partial response

PTT Partial Thromboplastin Time

QoL Quality of Life

RIT Radioimmunotherapy

RTX Rituximab

SAE Serious adverse event SAP Statistical analysis plan

s.c. Subcutaneous

SCID Severe combined immune deficient

SD Stable disease

SPD Sum of products of the 2 target tumour diameters SPECT Single Photon Emission Computed Tomography

SUV Standardized uptake value

SUSAR Suspected unexpected serious adverse reaction

TEAE Treatment emergent adverse event

TMF Trial Master File ULN Upper limit of normal

Y Yttrium

WHO World Health Organization
WHO PS WHO Performance Status
WOCBP Woman of Child Bearing Potential

## **Appendix 2: Study Governance Considerations**

#### **Regulatory and Ethical Considerations**

- This study will be conducted in accordance with the protocol and with the following:
- Consensus ethical principles derived from international guidelines such as the Declaration of Helsinki.
- Applicable ICH Good Clinical Practice (GCP) Guidelines
- Applicable laws and regulations
- The protocol, protocol amendments, ICF, Investigator Brochure, and other relevant documents (e.g., advertisements) must be submitted to an IEC/IRB by the Investigator and reviewed and approved by the IEC/IRB before the study is initiated.
- Any amendments to the protocol will require IEC/IRB approval before implementation of changes made to the study design, except for changes necessary to eliminate an immediate hazard to study patients.
- The Investigator will be responsible for the following:
- Providing written summaries of the status of the study to the IEC/IRB annually or more frequently in accordance with the requirements, policies, and procedures established by the IEC/IRB
- Notifying the IEC/IRB of SAEs or other significant safety findings as required by IEC/IRB procedures
- Providing oversight of the conduct of the study at the study site and adherence to requirements of 21 CFR, ICH guidelines, the IEC/IRB, European regulation 536/2014 for clinical studies (if applicable), and all other applicable local regulations

#### **Financial Disclosure**

Investigators and sub-Investigators will provide the Sponsor with sufficient, accurate financial information as requested to allow the Sponsor to submit complete and accurate financial certification or disclosure statements to the appropriate regulatory authorities. Investigators are responsible for providing information on financial interests during the course of the study and for 1 year after completion of the study.

#### **Informed Consent Process**

- The Investigator or his/her representative will explain the nature of the study to the patient or his/her legally authorised representative and answer all questions regarding the study.
- Patients must be informed that their participation is voluntary. Patients or their legally authorised representative will be required to sign a statement of informed consent that meets the requirements of 21 CFR Part 50, local regulations, ICH guidelines, Health Insurance Portability and Accountability Act (HIPAA) requirements, where applicable, and the IEC/IRB or study site.

• The medical record must include a statement that written informed consent was obtained before the patient was enrolled in the study and the date the written consent was obtained. The authorised person obtaining the informed consent must also sign the ICF.

- Patients must be re-consented to the most current version of the ICF(s) during their participation in the study.
- A copy of the signed ICF(s) must be provided to the patient or the patient's legally authorised representative.

Patients who are rescreened are required to sign a new ICF.

The ICF will contain a separate section that addresses the use of remaining mandatory samples for optional exploratory research. The Investigator or authorised designee will explain to each patient the objectives of the exploratory research. Patients will be told that they are free to refuse to participate and may withdraw their consent at any time and for any reason during the storage period. A separate signature will be required to document a patient's agreement to allow any remaining specimens to be used for exploratory research. Patients who decline to participate in this optional research will not provide this separate signature.

